## 8 Design

The **STOP-IT** trial is designed as a pragmatic, multi-centre, randomised, controlled, open-label, superiority study with two parallel groups and primary endpoints of opioid positivity and healthcare utilization at 12 months after enrollment. Randomization will be performed with a 1:1 allocation ratio using a stratified, permuted-block group schema according to the following strata (no fixed ratio):

- 1) RAAM clinic site (Barrie, Orillia, Midland, Wasaga Beach)
- 2) Severity of OUD according to DSM-V criteria (moderate vs severe)

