## 16 Allocation

### 16.1 Sequence generation

Participants will be randomly assigned to either Suboxone® or Sublocade® with a 1:1 allocation schema as per a computer-generated randomisation schedule stratified by RAAM clinic site and severity of OUD (moderate versus severe by DSM-V criteria) using permuted blocks of size 6 in each strata. A single block size was chosen since the next block size of 18 might be too large to allocate patients in a 1:1 ratio in the smaller RAAM clinics. The block size will not be disclosed to ensure concealment. Sufficient numbers of blocks will be prepared *a priori* to ensure sufficient coverage for all strata in the event that they have different sample sizes as there will be no *a priori* fixed ratio for enrollment in the different strata.

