## 20.11 Primary

### 20.11a Opioid positivity

We will use a 3-level hierarchical design to model the relapse-free weeks data where the observation for each week (Level 1) will be coded as binary; relapse-free week if urine drug screen and self-report is negative for non-prescribed opioid use, and otherwise relapse week if either is positive for non-prescribed opioid use. As described in Section 12.11, imputation of missing data will occur for those weeks in which a urine drug screen/self-report was not scheduled according to the results of the subsequent week's urine drug screen/self-report. Level 1 observations are clustered within individual participants (Level 2), which are nested within RAAM clinic sites (Level 3). We will analyse the outcome data using multi-level, mixed-effects logistic regression analysis with random effects estimated for the variance in the intercepts of both participant and clinic levels. The model will also include a random slope on the indicator for OUD severity (moderate versus severe) in the Level 2 random effects equation using an unstructured covariance structure between intercept and slope. We will also include clinic visit (week) and an interaction term between clinic visit and treatment. A sensitivity analysis will be conducted to compare this baseline model with an extended model that includes any baseline demographic or clinical variables that appear to be unbalanced at Level 1. The models will be compared using the likelihood-ratio comparison test for superiority. Post-regression analyses using *margins* command will be used to estimate difference in proportions of RFWs between treatment groups.

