## 20.12 Secondary outcomes

We will use a 3-level hierarchical design to model all the repeated measures outcomes (Medications Satisfaction Questionnaire and the WHOQOL-BREF) where the outcomes will be coded as continuous. Level 1 observations are clustered within individual participants (Level 2), which are nested within RAAM clinic sites (Level 3). We will analyse the data using multi-level, mixed-effects linear regression analysis with random effects estimated for the variance in the

intercepts of both participant and clinic levels. We will include a random slope on the indicator for OUD severity (moderate versus severe) in the Level 2 random effects equation using an unstructured covariance structure between intercept and slope. We will also include clinic visit and an interaction term between clinic visit and treatment, along with any baseline demographic or clinical variables that are unbalanced at Level 1.

Both clinic retention and mortality will be coded as binary outcomes. We will conduct unadjusted analyses for both using a chi-squared test (with continuity correction) or Fisher's exact test depending on cell sizes.

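### The participant-level random slope on OUD severity in 20.11a and 20.12 is not identified, and no severity fixed effect or fallback model is stated; the treatment contrast is essentially unaffected (minor)

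*Combined protocol and SAP*

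**What the plan says.** Section 20.11a models weekly relapse-free status with a three-level mixed logistic regression. It defines the levels as follows: "Level 1 observations are clustered within individual participants (Level 2), which are nested within RAAM clinic sites (Level 3". It then adds the slope: "The model will also include a random slope on the indicator for OUD severity (moderate versus severe) in the Level 2 random effects equation". The two participant-level terms are given a fully free covariance matrix. On the fixed part it says: "We will also include clinic visit (week) and an interaction term between clinic visit and treatment". The treatment result is a single quantity: the margins "command will be used to estimate difference in proportions of RFWs between treatment groups".

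Section 20.12 uses the same levels and covariance structure in linear models for the Medication Satisfaction Questionnaire and WHOQOL-BREF: "We will include a random slope on the indicator for OUD severity (moderate versus severe) in the Level 2 random effects equation".

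Severity is a randomisation stratum. Section 8 lists "Severity of OUD according to DSM-V criteria (moderate vs severe", and section 16.1 describes the schedule as "stratified by RAAM clinic site and severity of OUD (moderate versus severe by DSM-V criteria". It appears in the table of data taken before induction (18.11a) and not in the table of data taken during treatment (18.11b). Section 20.11b puts a severity indicator in the Poisson model. Sections 20.11a and 20.12 do not name one as a fixed effect, and neither gives a rule for a fit that fails or is singular.

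**The concern.** A random slope on a covariate describes how its effect varies between the units of a level, so the covariate must vary within those units. Severity does not vary within a participant. One parameter of the covariance matrix therefore has no information behind it, however many participants or visits there are.

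Three things are at stake. The slope variance and the covariance would be arbitrary numbers. Software may return no standard errors for them. And an analyst who meets a singular fit has no instruction on how to simplify it, while section 17 says that analysts know the allocation.

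Separately, a random slope with mean zero does not adjust the mean for severity. If no fixed effect accompanies it, the stratification factor is left out of the mean model.

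**Working it through.** The plan gives no figure to reproduce on this point. The check is algebra, followed by numerical confirmation under stated assumptions.

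**1. Algebra.** Let S = 0 (moderate) or 1 (severe), constant within a participant. The unstructured matrix has three parameters: intercept variance s0², covariance s01 and slope variance s1². The participant effect is b0 + b1·S. Since S² = S,

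Var(b0 + b1·S) = s0² + S·(2·s01 + s1²).

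- Moderate: s0².
- Severe: s0² + 2·s01 + s1².

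So s01 and s1² enter only through 2·s01 + s1². For example, (s0², s01, s1²) = (4, 0, 2), (4, -1, 4) and (4, -2, 6) give severe variances 4+0+2, 4-2+4 and 4-4+6. All equal 6, and the moderate variance is 4 each time. The same algebra applies to the linear models in 20.12.

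**2. One simulated trial.** Assumptions: 90 participants, 24 visits, s0² = 4, 2·s01 + s1² = 0.5; four fixed effects (intercept, treatment, week, week-by-treatment); clinic intercept left out.

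- The pairs (s01, s1²) = (-2.5, 5.5), (-1.5, 3.5), (-0.5, 1.5), (0, 0.5) and (0.2, 0.1) all give log-likelihood -1098.949. A two-dimensional integration that does not use the algebra gives -1098.9478 to -1098.9476.
- Any slope SD from √4.5 - √4 = 0.12 to √4.5 + √4 = 4.12 fits equally well.
- The information matrix has rank 6 for 7 parameters, with smallest eigenvalue about 1e-16. The null vector is -0.447 on s01, 0.894 on s1² and zero on every other parameter, so no fixed effect is involved.
- Setting s01 = 0 gives rank 6 for 6 parameters, with smallest eigenvalue 0.22. The standard errors of treatment and week-by-treatment are 0.561 and 0.389 both before (pseudo-inverse) and after.

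**3. The plan's weekly data structure.** There were 48 weekly rows. Unscheduled weeks were filled from the next visit, and a missed visit and the week before it were scored as not relapse-free (section 12.11). Assumptions: 15% of visits missed, 90 participants in clinics of 36/22/18/14, 60% severe, participant variances 4 and 6, clinic SD 0.5, log-odds ratios 1.3 for treatment and -0.7 for severity. The written random part was fitted with a severity fixed effect added, in 100 trials from three starting points each.

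- All 300 fits converged.
- The margins difference agreed between starts within 0.000002.
- The slope variance differed between starts at least 5.7-fold in every trial (median 52-fold).
- The smallest information eigenvalue was zero within 0.00004 in all 100.
- Two stratum variances, one parameter fewer, gave the same log-likelihood within 0.00001 and the same margins within 0.000002.

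**4. Leaving out the severity fixed effect.** For an assumed severity log-odds ratio of -0.7, the median treatment standard error rose by 1.3% (weekly structure) and 0.8% (24 visits). For -1.5 it rose by 4.4%. The mean shift in the RFW difference lay between -0.0006 and +0.0008.

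**5. Choice of repair.** One common participant variance was compared with two in 200 weekly trials. The RFW difference moved by a median of 0.005 (90th percentile 0.022), with mean shift -0.0006. Against the 0.15 target in section 14.4, the median is 0.005/0.15 = 3%.

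**The case against.** The strongest reply is that nothing the plan says it will report depends on the lost parameter. Section 20.11a takes one treatment quantity from this model, and that quantity is unaffected. Every test fit converged. This stands, and it caps the point at minor.

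A repair would also matter little on average: the typical shift is small against sampling error (the RFW difference had an SD of about 0.060 across simulated trials with 24 visits and equal true variances), and it shows no systematic direction. Section 32 promises public code and data, so a repair would be visible afterwards. Both replies stand, but visibility afterwards is not pre-specification.

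It can be said that a random slope normally accompanies a fixed one, so severity is implied. That is fair. The treatment main effect is not named either, so the text shows an incomplete list rather than a decision to omit severity.

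The extended model in 20.11a might be offered as the fallback. It is a sensitivity analysis that adds unbalanced baseline variables; it does not simplify the random part or apply to a failed fit.

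Perhaps Level 2 was meant to be the clinic. Both sections define it as the participant.

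**Conclusion.** The point holds as a minor defect of specification. Under the written levels, three covariance parameters describe two identifiable variances, so the slope variance and covariance are arbitrary and the information matrix is singular at any sample size. This needs no assumption beyond severity being fixed within a participant, which sections 8, 16.1, 18.11a and 18.11b support.

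Two stronger inferences are not supported. A reader might conclude that the primary comparison cannot be estimated or is biased. The null direction involves no fixed effect and the margins difference is essentially unchanged, given the usual treatment main effect. A reader might also conclude that the model will fail to converge. It did not in these fits, although they included a severity fixed effect and did not use STATA 17, the planned software. Missing standard errors and non-convergence remain possibilities, not findings.

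The size of the fixed-effect gap, about 1% in the treatment standard error at -0.7, and the size of the repair shift are indicative only, since they rest on the assumed simulation settings.

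**What to change.** In 20.11a and 20.12, replace the random-slope sentence with:

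> OUD severity is entered as a fixed effect, and the participant random intercept has a separate variance in each severity stratum (two parameters).

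This gives the same likelihood for the random part with one parameter fewer. List the fixed part in full: treatment, visit, visit-by-treatment and severity.

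Name one fallback in advance: a single common participant-intercept variance, with severity still a fixed effect. Its triggers should be:

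- non-convergence;
- a participant variance estimated at the boundary;
- a singular or non-positive-definite information matrix attributable to the participant variance terms.

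Non-convergence alone is too narrow. With 90% severe participants (median 9 moderate), the moderate variance fell below 0.05 in 3 of 100 simulated trials, and a converged fit can do this.

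If a clinic-level severity slope was intended, the text should say Level 3.

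The cost is two or three sentences in each section and no new data. When the true variances were equal, the SD of the RFW difference over 200 trials was 0.0600 with two variances against 0.0592 with one, so the extra variance costs almost nothing in precision.

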### 14.3 Healthcare utilization

In the only recent study that compared non-protocol-driven healthcare utilization using the incidence rates of healthcare days as an outcome measure among patients with OUD receiving opiate substitution therapy with either Sublocade® or placebo, the data demonstrated a combined emergency room visit or hospital day incidence rate of 2.01 healthcare days per 1 000 patient days in the Sublocade® group versus 6.97 healthcare days per 1 000 patient days in the placebo group. These rates likely underrepresent the current rates of healthcare utilization in Canada as the study was conducted in 2015 and the patients included in the trial were residents of the United States and 60% had no medical insurance likely creating barriers to healthcare access and lowered rates of utilization that would not exist for Canadian patients who have universal and free access to acute healthcare services. There have been no direct comparisons between Sublocade® and Suboxone® treatments. As a result, a sensitivity analysis

using different inputs has been conducted given that the maximum person days exposure for each patient is 365 days. We also assume a worse-case scenario of loss-to-follow-up (for any reason) of 50% over the study period, a rate of loss-to-follow-up much higher than the 20% rate reported by Ling *et al.*

**Table 4: Sensitivity analysis for attainable power to detect a range of differences in the incidence rates of healthcare days between treatment groups with different sample sizes**

Variable 	Scenarios	
	1	2
Comparator group incidence	2.0	2.4
Group difference in incidence rates	1.0	1.2
Sample size per group (patient days) 	3650	3650
Power	99	99

 Incidence = total number (hospital days + emergency room visits)/1 000 patient days; Assumptions: 2-sided  $\alpha$  level of 0.05; 50% loss-to-follow-up

 Sample size per group derived from a sample of 20 patients \* 365 days exposure/patient \* 0.5 (=50% rate of loss-to-follow-up)

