#### 14.4 Final sample size

In a hierarchical 3-level mixed effects model with 45 and 45 level 2 units (RAAM clinic patients) randomized to Suboxone® and Sublocade® in a 1:1 ratio, 4 level 3 units (RAAM clinics) in total and an average of 5 level 1 units (RFWs) per level 2 unit, 90.0% power is achieved to detect a difference in RFWs proportions of at least 0.15, where the Suboxone® and Sublocade® RFWs proportions are 0.3 and 0.45, respectively, assuming that the correlation between level 1 units in a level 2 unit is 0.8 and the correlation between level 2 units in a level 3 unit is 0.025, and the 2-sided test is performed at the 5% significance level. Using even a much smaller sample size (N=20 patients per group with 50% loss-to-follow-up over 12-month study period), a 2-sided comparison of two incidence rates (number of healthcare days per 1000 patient days exposure) with a sample size of 3650 patient days exposure per group would achieve 99% power at the 0.05 significance level to detect a difference in incidence rates of at least 1 if the Suboxone® group incidence rate was 2.

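### Sections 20.11a and 20.12 include treatment-by-visit without a participant random slope on week, so the interval for that term is too narrow; the averaged treatment difference is barely affected

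*Combined protocol and SAP*

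**What the plan says.** Section 20.11a models one binary row per week in a three-level logistic model with "random effects estimated for the variance in the intercepts of both participant and clinic levels". The one random slope is on OUD severity, at participant level. For time it adds: "We will also include clinic visit (week) and an interaction term between clinic visit and treatment". No random slope on week, serial correlation or robust variance is specified, and week is not said to be linear or categorical. The treatment comparison it names is a difference in proportions of relapse-free weeks obtained with margins.

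Section 20.12 repeats the structure in a linear model for the Medication Satisfaction Questionnaire and WHOQOL-BREF: "We will also include clinic visit and an interaction term between clinic visit and treatment". It names no margins contrast.

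Section 12.11 schedules a test every two weeks (24 over 48 weeks). Each unscheduled week takes the next test's result. A missed test makes both its own week and the week before it not relapse-free, while those weeks stay in the denominator as long as the patient is alive.

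**The concern.** Severity is a baseline factor, constant within a participant. A random slope on it changes how far participants' levels differ; it cannot describe one participant declining while another holds steady. All participants in an arm therefore share one time trend, and departures from it are treated as independent row-level noise.

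The section 12.11 rule produces such departures. A patient who stops attending becomes a run of failures to week 48, whatever came before. If a few more early leavers fall in one arm by chance, the arms' slopes differ, and the model credits that difference with the precision of many rows when only 90 patients inform it.

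At stake are the interval for treatment-by-week, any week-specific difference built from it, and any joint test of treatment plus interaction. In an open-label trial with unmasked analysts (section 17), this leaves open a spurious claim that the effect grows or fades.

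**Working it through.** **Plan's own figure.** The documents give no false-rejection rate for the interaction. The benchmark is the nominal level in section 14.4: "the 2-sided test is performed at the 5% significance level". The 90% power stated there concerns the difference in proportions, not this term.

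**Inputs from the documents**
- Section 14.4: "with 45 and 45 level 2 units (RAAM clinic patients) randomized to Suboxone", so 45 per arm.
- Section 14.4: "RFWs proportions are 0.3 and 0.45, respectively". The null runs use about 0.31 to 0.34 in both arms.
- Section 14.4: "assuming that the correlation between level 1 units in a level 2 unit is 0.8". On the logit scale the intercept variance is 0.8/0.2 × π²/3 = 13.2, an SD of about 3.6. SDs of 1.0 and 1.5 were also run as assumptions.
- Section 14.3: dropout of 50%, described as "a rate of loss-to-follow-up much higher than the 20% rate reported", giving a range of 20% to 50%.
- Sections 12.11 and 20.11a: 24 real tests, or 48 weekly rows after copying.

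**Assumptions.** Week is linear. Dropout is permanent, uniform in time, equal by arm and scored as relapse afterwards. There is no clinic effect or severity slope.

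**Fitted model.** logit P = β0 + β1·treatment + β2·week + β3·treatment×week + uᵢ, with uᵢ a participant intercept; maximum likelihood by quadrature. True β1 = β3 = 0. There were 600 trials per setting (Monte Carlo standard error at most √(0.5×0.5/600) = 2.0 points). Rejection at nominal 5%:

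| Dropout | Intercept SD | β3, 24 rows | β3, 48 rows | Averaged margins (24 / 48 rows) |
|---|---|---|---|---|
| 0% | 1.5 | 4.8% | 17.7% | 5.3% / 5.5% |
| 20% | 1.0 | 8.3% | not run | 6.2% / not run |
| 20% | 1.5 | 10.8% | 24.8% | 5.3% / 5.2% |
| 20% | 3.6 | 19.2% | 36.2% | 5.2% / 5.2% |
| 50% | 1.0 | 18.7% | not run | 5.3% / not run |
| 50% | 1.5 | 23.7% | 39.3% | 4.7% / 5.2% |
| 50% | 3.6 | 29.7% | 46.7% | 5.0% / 5.3% |

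With 24 rows and no dropout the test is correct, so dropout drives the 24-row inflation. With 48 rows, copying alone gives 17.7%, and dropout adds to it. A joint test of β1 and β3 rejected in 8% to 42% of trials across the dropout settings.

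Further runs of the same kind put the averaged margins difference mostly at 4% to 7%. One set with beta-distributed patient probabilities gave 5% to 8%. A margins difference read at week 48 rejected in 6% to 10% (24 rows) and 8% to 12% (48 rows).

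**With a participant random slope on week** (unstructured covariance, intercept SD 1.5, 300 trials per setting, same data for both models):

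| Setting | No slope on week | Slope on week |
|---|---|---|
| 20% dropout, 24 rows | 10.0% | 3.3% |
| 50% dropout, 24 rows | 18.3% | 4.0% |
| 50% dropout, 48 rows | 36.0% | 4.0% |

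**Quality of life (20.12).** WHOQOL-BREF has five times, weeks 0, 12, 24, 36 and 48. Rescaled to 0–1, Sxx = 0.25 + 0.0625 + 0 + 0.0625 + 0.25 = 0.625. Let τ be the SD of individual 48-week change divided by the residual SD. No document gives τ. The true variance of a participant's slope is 1/Sxx + τ². The random-intercept model takes it as (1 + τ²Sxx/4)/Sxx.
- τ = 0.5: 1.85/1.6625 = 1.113; 1.96/√1.113 = 1.86; two-sided error about 6%.
- τ = 1: 2.60/1.85 = 1.405; 1.96/√1.405 = 1.65; about 10%.
- τ = 1.5: 3.85/2.1625 = 1.780; 1.96/√1.780 = 1.47; about 14%.

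Medication satisfaction was not calculated.

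**The case against.** The strongest reply is that the plan never tests the interaction. It only includes it; the comparison it names is the margins difference, and the hypotheses and objectives (sections 6 and 7) ask no time-course question. The likelihood-ratio test in 20.11a compares covariate sets, not this term. This stands, and it limits the harm to readings beyond the averaged difference. It does not settle the matter: 20.11a does not say whether margins is averaged or taken at one week, sections 8 and 12.11 speak of 12 months, and 20.12 names no contrast, leaving its treatment effect undefined once the interaction is in the model.

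Second, the inputs are assumptions. The dropout figures come from the healthcare-utilization calculation, and 50% is offered there as a pessimistic case. Withdrawal need not end testing either: section 18.22 continues follow-up through routinely collected data, and 18.11b lists urine toxicology and Timeline Followback as routine. This stands as a caution about size. Patients who stop attending would still score as failures.

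Third, participant-clustered standard errors look like an easier remedy. They gave 4.3% to 6.0% in the dropout settings, but without a clinic level. With the planned clinic intercept, participants in one clinic share a random effect, so the independent units are the four clinics. That remedy is unchecked for the planned model and should not be relied on.

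**Conclusion.** The concern holds for the treatment-by-week term. Its model-based interval is too narrow because individual time trends are not modelled. In the primary model, under the stated assumptions, false rejection is about 8% to 30% on 24 fortnightly rows and about 25% to 47% on the planned 48 rows with dropout, against about 5% on 24 rows without dropout. Part of the 48-row figure is due to copied weeks.

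Three stronger readings are tempting and not supported:
- That the primary comparison is invalid. The averaged margins difference stays near 5% to 7%; only a week-48 reading is modestly inflated (about 6% to 12%).
- That the plan has one fixed false-positive rate. The rate moves with dropout, intercept SD and row count, none of which the plan fixes for this term.
- That these percentages carry over to 20.12. Scoring dropout as failure belongs to the primary outcome alone. For quality of life the error is about 6% to 14% if the SD of individual change is 0.5 to 1.5 times the residual SD.

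The correction should be made. It matters most in 20.12, where no averaged contrast is named. No calculation included the clinic intercept or the severity slope.

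**What to change.** In both 20.11a and 20.12:
1. Add a participant-level random slope on week, and say whether week is linear or categorical in the fixed part.
2. State that the treatment contrast is the difference averaged over follow-up, obtained from margins, and that treatment-by-week is supportive.
3. Do not substitute participant-clustered standard errors while the clinic random intercept is kept.

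This takes a sentence or two per section and no new data. The price is wider intervals for time-course terms and a harder fit. Kept beside the severity slope with unstructured covariance, the participant level would have three variances and three covariances to estimate from 90 patients. A fallback for non-convergence should therefore be written down in advance. The simulated error of 3% to 4% with the slope was obtained without the clinic level and should be rechecked in the full model.
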